### Other Toxicities

For the first occurrence of any nonhematologic Grade 2 chemotherapy-related toxicity (except alopecia), trilaciclib or placebo + E/P should be withheld until the toxicity recovers to Grade 1 or baseline. Treatment may then be resumed at the same dose level. For the second occurrence of any nonhematologic Grade 2 chemotherapy-related toxicity (except alopecia), following recovery of the toxicity to Grade 1 or baseline, E/P should be resumed at dose level -1; for the third occurrence, the E/P doses should be reduced to dose level -2. A fourth occurrence will result in discontinuation of trilaciclib or placebo + E/P therapy. No dose reduction should be made for Grade 1 toxicities.

For any Grade 3 or 4 chemotherapy-related toxicities not mentioned above, trilaciclib or placebo + E/P should be withheld until the toxicity recovers to Grade 1 or baseline. Treatment should then be resumed at dose level -1 for the first occurrence and dose level -2 for the second occurrence. A third occurrence will result in discontinuation of trilaciclib or placebo + E/P therapy.

#### 8.4.5.3. Atezolizumab

A list of the AESI for atezolizumab is provided in [Appendix 3](#) and these should be reported using the same process and timeline as SAE reporting (see Section [11.4.1.10](#)).

No dose reductions will be allowed for atezolizumab during the study. Management of irAEs may include administration of corticosteroids, delay of a scheduled dose, or discontinuation of therapy. Please refer to the Atezolizumab Guidance for the Investigator ([Appendix 1](#)) and the full atezolizumab prescribing information ([Appendix 2](#)) for guidance on the management of irAEs.

Atezolizumab has been associated with risks such as the following: IRRs; immune-related hepatitis, pneumonitis, colitis, pancreatitis; diabetes mellitus; hypothyroidism; hyperthyroidism; adrenal insufficiency; Guillain-Barré syndrome; myasthenic syndrome or myasthenia gravis; hypophysitis; and meningoencephalitis. In addition, systemic immune activation is a potential risk associated with atezolizumab when given in combination with other immunomodulating agents. Refer to the Atezolizumab Guidance for the Investigator ([Appendix 1](#)) for a detailed description of anticipated safety risks for atezolizumab and their management.

For patients enrolled with baseline AST and ALT  $\geq 3 \times$  ULN in the presence of liver metastases, if further increase in AST and ALT occurs, atezolizumab should be held until the patient is discussed with the medical monitor.

Systemic immune activation is a rare condition characterized by an excessive immune response. Given the mechanism of action of atezolizumab, systemic immune activation is considered a potential risk when given in combination with other immunomodulating agents. Systemic immune activation should be included in the differential diagnosis for patients who, in the absence of an alternative etiology, develop a sepsis-like syndrome after administration of atezolizumab, and the initial evaluation should include the following:

- CBC with peripheral smear
- Prothrombin time, partial thromboplastin time, fibrinogen, and D-dimer
- Ferritin
- Triglycerides
- AST, ALT, and total bilirubin
- Lactate dehydrogenase
- Complete neurologic and abdominal examination (assess for hepatosplenomegaly)

Other irAEs attributed to atezolizumab not listed above should be assessed by the investigator and discussed with the medical monitor to determine if atezolizumab should be held or discontinued.

If corticosteroids have been initiated as part of the irAE management, they must be tapered over  $\geq 1$  month to  $\leq 10$  mg/day oral prednisone or equivalent before atezolizumab can be resumed. If the delay for re-starting atezolizumab is  $> 15$  weeks for recovery from immune-related toxicities attributed to atezolizumab (12 weeks for recovery to  $\leq$  Grade 1 and up to an additional 3 weeks for steroid taper of oral prednisone or equivalent to  $\leq 10$  mg/day), atezolizumab will be permanently discontinued.

**Discontinuation or interruption of trilaciclib or placebo + E/P does not preclude continuation of atezolizumab and vice versa. For instance, if an AE is attributed to trilaciclib or placebo, etoposide, or carboplatin (eg, hematologic toxicity) during the induction part of the study, then atezolizumab will be continued while the trilaciclib or placebo + E/P are held. While the trilaciclib or placebo + E/P are held, the patient will continue to receive atezolizumab, be monitored for safety (see Section 10.3.4), and will begin the next trilaciclib or placebo + E/P/A-containing induction cycle after the toxicity resolves. If the AE is immune related and attributed to atezolizumab; then trilaciclib or placebo + E/P will be continued for up to 4 induction cycles while the atezolizumab is held.**

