Atezolizumab has been associated with risks such as the following: infusion-related reactions (IRRs); immune-related hepatitis, pneumonitis, colitis, pancreatitis; diabetes mellitus; hypothyroidism; hyperthyroidism; adrenal insufficiency; Guillain-Barré syndrome; myasthenic syndrome or myasthenia gravis; hypophysitis; and meningoencephalitis. In addition, systemic immune activation is a potential risk associated with atezolizumab when given in combination with other immunomodulating agents. Refer to the Atezolizumab Guidance for the Investigator ([Appendix 1](#)) for a detailed description of anticipated safety risks for atezolizumab and their management.

Management of immune-related adverse events (irAEs) attributed to atezolizumab may include administration of immunosuppressant medications like corticosteroids, etc.; delay of a scheduled dose; or discontinuation of therapy. No dose reductions will be allowed for atezolizumab. Atezolizumab dosing will be held in the event of any irAEs attributed to atezolizumab until the event has improved to  $\leq$  Grade 1. See the Atezolizumab Guidance for the Investigator ([Appendix 1](#)).

Other irAEs attributed to atezolizumab not listed above should be assessed by the investigator and discussed with the medical monitor to determine if atezolizumab should be held or discontinued. If the irAE does not improve to  $\leq$  Grade 1 within 12 weeks, treatment will be permanently discontinued.

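### Section 8.4.5.3 requires a steroid taper of at least 1 month before atezolizumab resumes, but its 15-week delay limit allots only 3 weeks for that taper and does not say when the taper starts

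*Protocol*

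**What the plan says.** Two consecutive sentences of Protocol section 8.4.5.3 govern the restart of atezolizumab after an immune-related adverse event (irAE).

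- The first sets a minimum taper of 1 month: "If corticosteroids have been initiated as part of the irAE management, they must be tapered over" at least that long, to no more than 10 "mg/day oral prednisone or equivalent before atezolizumab can be resumed".
- The second sets the stopping limit. If the delay exceeds 15 "weeks for recovery from immune-related toxicities attributed to atezolizumab", then "atezolizumab will be permanently discontinued". The 15 weeks are broken down as "12 weeks for recovery to" Grade 1 or less, and "up to an additional 3 weeks for steroid taper of oral prednisone or equivalent" to the same 10 mg/day or less.

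The 12 + 3 week split is repeated in the synopsis (Criteria for Subsequent Cycles and Study Duration), in Protocol 6.1.1, 10.3.2 and 10.3.3, and in the SAP under the criteria for starting Cycle 2 and later induction cycles. None of these places gives the 1-month minimum. Sections 6.1.1, 10.3.2 and 10.3.3 do point the reader to 8.4.5.3.

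The synopsis also says that an irAE not improved to "Grade 1 within 12 weeks, treatment will be permanently discontinued". That sentence follows one about irAEs outside the listed set, and it contains neither the 3-week nor the 15-week figure.

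**The concern.** Both sentences describe the same taper, to the same dose, in the same patient. One gives it a minimum of about a month; the other budgets at most 3 weeks for it. The word *additional* suggests that the taper follows the recovery period, yet no section says from which event it is counted.

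Two things are at stake. A patient who recovers late, but inside the stated recovery time, may be unable to complete the required taper before the permanent stopping limit. And a reader relying only on the words of 6.1.1, 10.3.2 or 10.3.3 would take a 3-week taper as compliant, while a reader of 8.4.5.3 would not. For the patient concerned the result is either permanent loss of the only maintenance drug or a resumption that departs from a mandatory condition.

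**Working it through.** **Inputs.** From 8.4.5.3: recovery allowance 12 weeks (84 days), taper allowance 3 weeks (21 days), delay limit 15 weeks (105 days), minimum taper 1 month. The documents do not define a month in days, so 28 to 31 days is assumed. Recovery and total delay are assumed to run from the same starting point, as the 12 + 3 breakdown implies.

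**Step 1: reproduce the stated limit.** 12 + 3 = 15 weeks, or 84 + 21 = 105 days. The plan's figure is reproduced.

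**Step 2: compare the two taper figures.** Shortfall = minimum taper − 21 days.

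**Step 3: put the minimum taper in place of the 3 weeks, with the taper starting at recovery.** Total for recovery at week 12 = 84 + taper days. Latest recovery that still fits = 105 − taper days.

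| Month taken as | Shortfall against 21 days | Total if recovery is at week 12 | Excess over 105 days | Latest recovery that fits |
|---|---|---|---|---|
| 28 days (4.00 wk) | 7 days | 112 days (16.00 wk) | 7 days | day 77 (week 11.0) |
| 30 days (4.29 wk) | 9 days | 114 days (16.29 wk) | 9 days | day 75 (week 10.7) |
| 31 days (4.43 wk) | 10 days | 115 days (16.43 wk) | 10 days | day 74 (week 10.6) |

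Under this sequence the last 1.0 to 1.4 weeks of the 12-week recovery allowance cannot be followed by the minimum taper within 15 weeks. Earlier recoveries leave room for it.

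**Step 4: let the taper start before recovery.** A minimum taper begun by day 74 to 77 ends by day 105. A patient whose event reaches Grade 1 or less only at week 12 would then satisfy both sentences. The outcome therefore turns on the unstated start point.

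**Step 5: rough size.** The Table 4-1 rows available to this review report steroid use in 34 (pneumonitis), 5 (hepatitis), 10 (colitis), 2 (pancreatitis), 6 (adrenal insufficiency) and 2 (Guillain-Barré syndrome) of 2160 patients. The sum is 59, and 59/2160 = 2.7%. Applied to 106 patients this gives 0.027 × 106 = 2.9. It assumes no patient is counted twice and that the tabulated rates carry over to this combination. The adrenal cases may reflect replacement therapy; without them, 53/2160 = 2.5%, or about 2.6 patients. These are patients who might face a taper at all, not patients in the affected window.

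**The case against.** The strongest reply is that the sentences are not strictly incompatible. The first is a condition for resuming and the second is a stopping rule. A site can obey both by stopping atezolizumab once the delay passes 15 weeks, and nothing promises that recovery by week 12 secures resumption. The taper's start is not fixed either, so the 3 weeks could be read as time after week 12 to finish a taper already under way. All of this stands. A reader might infer that sites must break one rule; the documents do not support that.

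Second, other text may help. Section 8.1, which covers delays for toxicity as well as administrative ones, requires a total atezolizumab delay over 15 weeks to be discussed with the medical monitor. Sections 6.1.1, 10.3.2 and 10.3.3 carry a similar clause, but in the sentence on administrative delays. irAE management is also referred to the Appendix 1 guidance and the prescribing information, whose text was not available to this review and may define the taper's start. Discussion with the monitor makes unnoticed divergence between sites less likely. It does not cancel the instruction to discontinue, and it does not tell the monitor which taper figure governs.

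Third, the effect is small. Table 4-1 gives median event durations of 1.5 months for pneumonitis, 1 month for hepatitis, 1.4 months for colitis and 19 days for pancreatitis, mostly well short of week 10.6. Guillain-Barré syndrome, at 4.6 months, is longer but rare (5 of 2160). This limits the consequence; it does not remove the mismatch in the text.

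**Conclusion.** The inconsistency is real and confined to wording. Section 8.4.5.3 sets a minimum taper 7 to 10 days longer than the allowance in its own next sentence, and the shorter figure alone is repeated in four other places in the protocol and one in the SAP.

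The forced permanent stop is conditional. It requires steroid treatment, a taper that starts at recovery to Grade 1 or less, and recovery between about week 10.6 to 11.0 and week 12. About 3 of 106 patients might need a taper, on the assumptions shown, and fewer would recover in that window.

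A reader might also infer that PFS or OS results would depend on which sentence a site followed. The numbers do not support that: very few patients are involved, both arms receive atezolizumab under the same rules, and assignment is blinded. The primary endpoints concern neutropenia during induction; the sample size, alpha and power do not use these figures.

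**What to change.** In 8.4.5.3, reconcile the minimum taper, the taper allowance and the 15-week total, and state the event from which the taper is counted (for example, steroid start, or recovery to Grade 1 or less). Check the result against the Appendix 1 guidance. Then carry the same wording to the synopsis (Criteria for Subsequent Cycles and Study Duration), 6.1.1, 10.3.2, 10.3.3 and the matching SAP text. Which figures and which start point to adopt is a clinical decision for the sponsor, and this review does not propose one.

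The cost is a protocol wording change and one matching SAP phrase. No visits, assessments, data items or analyses are added.

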## 8.5. Randomization and Blinding

The study is randomized and blinded. Patients meeting all inclusion and exclusion criteria will be randomized 1:1 to receive trilaciclib or placebo with E/P/A therapy by an IWRS according to a randomization schedule generated by an unblinded statistician. Randomization will be stratified by ECOG performance status (0 to 1 versus 2) and presence of brain metastases (yes versus no). Each patient will be assigned a unique randomization number, which will not be reused.

Each site will have an unblinded pharmacist/designee, who will have access to the treatment assignment to label and distribute the blinded study drug. The patients, investigators, other site staff involved in the clinical care of the patients, and the sponsor or designees involved in the conduct of the study will not be aware of the treatment group to which a particular patient has been randomized. If an investigator determines that a patient's assignment should be unblinded for reasons of safety, this should be discussed with the medical monitor prior to unblinding, unless an urgent and immediate intervention is required that precludes this discussion. If unblinding of the treatment assignment is necessary, the investigator will

obtain the treatment assignment details from the IWRS. Any unplanned unblinding must be communicated to the project manager and study statistician for documentation in the study files and the clinical study report.

## 8.6. Prior and Concomitant Medications and Procedures

All concomitant medications including prescription medications, over-the-counter preparations, growth factors, blood products, and parenteral nutrition taken during the 14 days before the date of enrollment, during the study treatment, and through 30 days after the last dose of study drug will be documented. Documentation will include information regarding start and stop dates, dose(s), and reasons for the medication use.

Administration of other concomitant nonprotocol anticancer therapies prior to progression is not permitted while on this study.

Administration of other concomitant investigational agents for any indication is not permitted while on this study.

Palliative radiation therapy or surgery is allowed to control disease symptoms but not to aid in the response of the tumor and patients requiring palliative radiation may continue receiving study drug administration if they meet the requirements described in Section 11.1.4. However, for patients who have not had disease progression, the requirement for palliative radiation therapy or surgery will be regarded as disease progression.

Caution should be exercised when administering etoposide phosphate with drugs that are known to inhibit phosphatase activities (eg, levamisole hydrochloride). Although carboplatin has limited nephrotoxic potential, caution should be exercised when administering carboplatin with aminoglycosides, which has resulted in increased renal and/or audiologic toxicity. Any medication that is contraindicated when using etoposide or carboplatin is not permitted, and special warnings and precautions for use of carboplatin and etoposide should be observed.

Necessary supportive care such as antiemetics, antidiarrheals, etc., per the standard of care at the study center will be permitted. **Administration of hematopoietic growth factors in Induction Cycle 1 will not be permitted (ie, no growth factors should be used prior to the actual Induction Cycle 2 Day 1 dosing visit; Section 8.4.5.2).** However, hematopoietic growth factors may be utilized in subsequent cycles at the investigator's discretion as stated in Section 8.4.5.2. To reduce potential immune system interactions, the use of dexamethasone as an antiemetic should be minimized where possible.

For the purposes of this trial, concomitant medications like bisphosphonates and denosumab, which are used to prevent skeletal-related events in patients with bony metastases, are allowed as long as the patient has been on stable doses for at least 4 weeks.

Trilaciclib is a time-dependent inhibitor of CYP3A4 and is a substrate for CYP3A4. Trilaciclib exposure may be altered by concomitant use of drugs that are strong CYP3A inhibitors or inducers. The exposure of drugs that are CYP3A substrates may be altered by concomitant use of trilaciclib (Section 4.4.2).

- Caution should be exercised with concomitant use of drugs that are strong CYP3A inhibitors (eg, aprepitant, clarithromycin, itraconazole, ketoconazole, nefazodone, posaconazole, telithromycin, verapamil, and voriconazole).
- Caution should be exercised with concomitant use of drugs that are strong or moderate CYP3A inducers (eg, phenytoin, rifampin, carbamazepine, St John's Wort, bosentan, modafinil, and nafcillin).
- Caution should be exercised with concomitant use of drugs that are extensively metabolized by CYP3A.

Trilaciclib is a potent inhibitor of MATE1, MATE2-K, OCT2 membrane transporters and therefore caution should be exercised with concomitant use of drugs that are substrates for these transporters (Section 4.4.2).

Cytochrome P450 enzymes, as well as conjugation/glucuronidation reactions, are not involved in the metabolism of atezolizumab. No drug interaction studies for atezolizumab have been conducted. There are no known interactions with other medicinal products or other form of interactions (Section 1.10 of the Atezolizumab Guidance for the Investigator, [Appendix 1](#)).

Atezolizumab should not be given to patients with a condition requiring systemic treatment with either corticosteroids (> 10 mg daily prednisone equivalents) or other immunosuppressive medications (including but not limited to cyclophosphamide, azathioprine, methotrexate, thalidomide, and anti-TNF agents) within 14 days of atezolizumab administration. Inhaled or topical steroids and adrenal replacement doses > 10 mg daily prednisone equivalents are permitted in the absence of active autoimmune disease.

Any diagnostic, therapeutic, or surgical procedures performed during the study period will be documented. Documentation will include information regarding the date(s), indication(s), description of the procedure(s), and any clinical or pathological findings.

Medications will be coded using the most recent World Health Organization (WHO) Drug Dictionary version.

## **8.7. Transfusions**

Platelets should be transfused at a threshold of  $\leq 10,000/\mu\text{L}$ . Platelets should also be transfused in any patient who is bleeding with a platelet count  $< 50,000/\mu\text{L}$  (100,000/ $\mu\text{L}$  for central nervous system or ocular bleeding). Please also refer to the American Society of Clinical Oncology (ASCO) guidelines ([Schiffer 2001](#)).

Patients with hemoglobin  $< 8.0$  g/dL or with symptomatic anemia can be treated with RBC transfusions at the investigators discretion.

## **8.8. Prophylactic Cranial Irradiation**

Prophylactic cranial irradiation for patients without detectable brain metastases has been shown to decrease the frequency of subsequent intracranial relapse and improve survival for patients with SCLC ([Aupérin A 1999](#); [Slotman 2007](#)). Therefore, patients with a confirmed CR are strongly encouraged to receive PCI after completion of induction chemotherapy. Patients with a confirmed PR should also consider PCI after completion of induction chemotherapy based on the investigator's judgment. Following the completion of the induction part, PCI may be administered concurrently with atezolizumab during the maintenance part.

## **8.9. Treatment Compliance**

The investigator or designee will dispense the study drugs, via an unblinded pharmacist/designee, only for use by patients enrolled in the study as described in this protocol. The study drugs are not to be used for reasons other than those described in this protocol. The investigator or other study staff will supervise each dose of the study drugs administered in the clinic. The clinical study site will maintain records of study drugs receipt, preparation, and dispensing, including the applicable lot numbers; patient's height, body weight, and BSA; date and time of the start and end of each trilaciclib or placebo, etoposide, carboplatin, and atezolizumab infusion; and total drug administered in milligrams. Any discrepancy between the calculated dose and dose administered and the reason for the discrepancy will be recorded on the electronic case report form (eCRF) and in the source documents.

## 9. STUDY FLOWCHART

The procedures and assessments to be performed during the study are outlined in [Table 9-1](#). The timing and number of samples collected for PK, immunologic markers and anti-atezolizumab antibody testing may be altered based on emerging data without requiring an amendment if the blood volume/day or overall does not increase and the patient is not required to have additional clinic visits or prolongation of a clinic visit, ie, the risk-benefit profile for the patient does not worsen. The investigators and institutional review boards (IRBs) or Independent Ethics Committees (IECs) will be notified if the frequency is reduced.

**Table 9-1 Schedule of Assessments**

Cycle Day	Screening	Enroll	Induction (21-day cycles) a										Last Induction Cycle	Maintenance (21-day cycles) b		Post-Treatment Visits c		Survival Follow-up d		
			Induction Cycles 1 and 3					Induction Cycles 2 and 4						Maintenance Cycle 1 and Odd Cycles	Maintenance Cycle 2 and Even Cycles					
			1	2	3	8	15	1	2	3	8	15				22	1		1	30 (+3)
Informed Consent e	X																			
Demographics	X																			
Medical History f	X																			
Eligibility Eval.	X	X																		
Performance Status	X		X					X						X	X	X	X			
Physical Exam	X		X					X						X	X	X	X			
Height, Weight & Vital Signs g	X		X		X			X		X				X	X	X	X			
Electrocardiogram	X												X							
Clinical Chemistry	X		X h					X h						X h	X h	X	X			
TSH, free T4, and free T3	X							X							X	X	X			
Hematology	X		X i		X	X	X	X i		X	X	X	X	X i	X i	X	X			
Urinalysis	X		X h					X h						X h	X h	X	X			
Pregnancy test j		X j														X	X			
Randomization k		X																		
Tumor Assessment l	X l2											X			X	X l1,l2	X l1,l2	X l1		
Archived Tumor Sample m		X																		
Trilaciclib or Placebo n			X	X	X			X	X	X										
Carboplatin			X					X												
Etoposide			X	X	X			X	X	X										
Atezolizumab			X o					X o						X	X					
██████████			█					█						█	█	█	█			
PK q (Trilaciclib, Etoposide, Carboplatin)			X																	

Cycle Day	Screening	Enroll	Induction (21-day cycles) a										Last Induction Cycle	Maintenance (21-day cycles) b		Post-Treatment Visits c		Survival Follow-up d
			Induction Cycles 1 and 3					Induction Cycles 2 and 4						Maintenance Cycle 1 and Odd Cycles	Maintenance Cycle 2 and Even Cycles			
	-14	-3 to 1	1	2	3	8	15	1	2	3	8	15	22	1	1	30 (+3)	90 (+7)	
Atezolizumab PK f			X					X							X	X	X	
Immunologic Marker s			X s											X s			X s	
Anti-atezolizumab Antibody Testing t			X					X							X	X	X	
AEs u	X u		X u													X u		
Con. Medications	X		X															
Survival Follow-up d																		X

AE = adverse event; Eval. = evaluation; [REDACTED]; irRECIST = immune-related RECIST; [REDACTED]; PK = pharmacokinetics; RECIST v1.1 = Response Evaluation Criteria in Solid Tumors, Version 1.1; T3 = tri-iodothyronine; T4 = thyroxine; TSH = thyroid-stimulating hormone

- a During the induction part, study drug administration (trilaciclib or placebo plus E/P/A) will continue for up to four 21-day cycles or until disease progression per RECIST v1.1, unacceptable toxicity, withdrawal of consent, or discontinuation by investigator, whichever occurs first. Following disease progression per RECIST v1.1, if the patient appears to be deriving clinical benefit, the investigator believes it is in the best interest of the patient, and the patient has provided re-consent, study drug administration may be continued until loss of clinical benefit.
- b During the maintenance part, study drug administration (atezolizumab) will continue in 21-day cycles until disease progression per RECIST v1.1, unacceptable toxicity, withdrawal of consent, or discontinuation by investigator, whichever occurs first. Following disease progression per RECIST v1.1, if the patient appears to be deriving clinical benefit, the investigator believes it is in the best interest of the patient, and the patient has provided re-consent, study drug administration may be continued until loss of clinical benefit.
- c Patients will return to the study center for post-treatment visits at 30 (+3) and 90 (+7) days after the last dose of study drug.
- d Monthly phone calls will be made to each patient that is in the Survival Follow-up Phase. Patients will be followed for survival until at least 70% of the patients have died. Any anticancer therapies used will be collected.
- e Informed consent may be obtained up to 28 days prior to the first study treatment administration.
- f Including medical, surgical, radiation history, smoking history, family history, documentation of tumor diagnosis, baseline signs and symptoms within 4 weeks prior to randomization, weight loss in the 6 months prior to randomization ( $\leq 5\%$  or  $> 5\%$ ), and medications taken within 14 days of enrollment.
- g Height will only be measured at the screening visit. Weight will only be measured at the screening visit and on Day 1 of each cycle. Body surface area calculation (based on actual body weight) will be completed on Day 1 of each cycle and vital signs obtained within 15 minutes before and after trilaciclib or placebo and E/P/A infusions. Vitals only need to be taken before the trilaciclib or placebo infusion, between each subsequent infusion, and after the last infusion on Days 1 and 3.
- h Clinical chemistry (albumin, alkaline phosphatase, total bilirubin, calcium, chloride, creatinine, glucose, inorganic phosphorus, potassium, total protein, ALT, AST, lactate dehydrogenase [LDH], sodium, and blood urea nitrogen [BUN], amylase, lipase) and urine analysis may be obtained up to 72 hours prior to the first dose of each cycle of trilaciclib or placebo + E/P/A therapy (induction part) or atezolizumab (maintenance part).
- i Hematology will be obtained (hemoglobin, white blood cells (WBC) with differential, and platelet counts). Hematology may be obtained up to 24 hours prior to first dose of each cycle of trilaciclib/placebo + E/P/A therapy (induction part) or atezolizumab (maintenance part).
- j For female patients of childbearing potential: serum  $\beta$ -hCG at enrollment; and serum or urine  $\beta$ -hCG obtained at the post-treatment visits.

- k Randomization is to be done within 3 days prior to first dose of trilaciclib or placebo + E/P/A therapy, following confirmation that the patient is eligible for the study.
- l For tumor assessment, all sites of disease should be assessed radiologically by CT or MRI at screening and after every even cycle for 9 months of the study (ie, approximately every 6 weeks) and after every third cycle (ie, approximately every 9 weeks) thereafter while receiving study drug, until the occurrence of disease progression. Additional scans may be obtained at the discretion of the investigator, if clinically indicated. If a patient shows a radiological response (CR or PR), a confirmatory radiological assessment will be performed at least 4 weeks after the response was first noted. Assessments should be performed within 7 days of starting the subsequent cycle. The same method of assessment (CT or MRI) should be used to characterize tumors at screening and at all follow-up assessments. If positron emission tomography is used, it should also be accompanied by spiral CT or MRI.
- l1: At the post-treatment visits at 30 (+3) and 90 (+7) days after the last dose of study drug, obtain tumor assessment for patients who have not progressed at the time of study drug discontinuation (may be performed within 4 weeks). For those patients in the survival follow-up who have not progressed at the time of study drug discontinuation, tumor assessments, including all sites of disease, will be assessed radiologically by CT or MRI, as performed at screening, every 2 months (approximately 60 ± 7 days) until the occurrence of progressive disease or study completion.
- l2: Brain scans with contrast (by CT or MRI) to be obtained with tumor assessment at screening (within 28 days of dosing). Patients without the presence of brain metastases at screening should also have a brain scan at the end of the induction part. Patients with brain metastases at screening should have brain scans with every scheduled tumor assessment.
- m Archived tumor samples should be available for banking for assessment of relevant DNA, ribonucleic acid (RNA), and protein markers, such as PD-L1 or those involved in the CDK4/6 pathway. Tumor samples may be banked for up to 10 years.
- n Trilaciclib or placebo will be administered as an IV infusion in 250 mL of D5W or sodium chloride solution 0.9% over approximately 30 minutes prior to E/P chemotherapy on Days 1 to 3 of every induction cycle. If there is any volume remaining in the trilaciclib or placebo infusion bag at the end of the 30 minutes, the infusion should be continued at the same rate until the entire contents of the bag have been administered to ensure patients receive the full dose. The interval between doses of trilaciclib or placebo on successive days should not be greater than 28 hours. The interval between the dose of trilaciclib or placebo and the first dose of chemotherapy on a given day (etoposide or carboplatin) should not be greater than 4 hours. Trilaciclib or placebo will only be administered with chemotherapy. If administration of E/P chemotherapy is discontinued, trilaciclib or placebo should also be discontinued. Chemotherapy cannot be administered until after completion of the trilaciclib or placebo infusion. If the second or third dose of trilaciclib in any given cycle is not administered for any reason, do not administer the dose of etoposide or carboplatin chemotherapy on that day. After discontinuation of study drug, patients should be strongly encouraged to complete all scheduled assessments through the end of their current 21-day treatment cycle, [REDACTED]; CBC assessment on Day 22; the Post-Treatment Visits; and the Survival Follow-up Phase of the study.
- o During the induction part, atezolizumab should be administered following the administration of trilaciclib or placebo, etoposide, and carboplatin.
- p Patient-reported outcomes should be completed at Days 1 of each cycle and at the post-treatment visits at 30 (+3) and 90 (+7) days after the last dose of study drug. [REDACTED]
- q At least 5 patients enrolled in each treatment group will have trilaciclib, etoposide, and carboplatin PK samples collected on Day 1 of Induction Cycles 1 and 3 at the time points specified.
- r Blood samples will be collected from all patients predose and 30 minutes after the end of atezolizumab infusion to determine the minimum and maximum observed serum atezolizumab concentration on Day 1 of Induction Cycles 1, 2, 3, and 4; Maintenance Cycles 4, 8, 12, and every eighth cycle thereafter; and at 30 (+3) and 90 (+7) days after the last dose of study drug.
- s Peripheral blood samples will be collected at predose on Day 1 of Induction Cycle 1, Day 1 of Maintenance Cycle 1 (first cycle of maintenance part), Day 1 of Maintenance Cycle 5, and at the post-treatment visit at 90 (+7) days after the last dose of study drug.
- t Anti-atezolizumab therapeutic antibodies will be measured predose on Day 1 of Induction Cycles 1, 2, 3, and 4; Maintenance Cycles 4, 8, 12, and every eighth cycle thereafter; and at 30 (+3) and 90 (+7) days after the last dose of study drug.
- u Adverse events will be recorded from the time of informed consent. AEs will be collected through 30 days after the last dose of study drug; SAEs and AESI will be collected through 90 days after the last dose of study drug. All AEs should be followed until they are resolved, have returned to baseline, or it is deemed that further recovery is unlikely.

